#### **Study Protocol**

## **Purpose**

The purpose of this study is to assess, prospectively, the effect of email reminders for well-child check (WCC) visits on adherence to these visits among those who have not yet scheduled the visit. The investigators hypothesize that sending reminders will increase scheduling WCC visits, attending WCC visits, and being up to date for the child's required immunizations beyond what occurs in the absence of these reminders.

### **Background**

Regular attendance at recommended WCC visits is associated with having up-to-date immunizations. Standard care involves scheduling a follow-up WCC visit at the end of the current visit. However, if the child's parents do not choose to schedule a follow-up visit at that time or miss a WCC visit, they may not be offered another easy opportunity to schedule one. That is, they would have to remember to schedule a visit and contact the clinic proactively.

In this study, 30 days before a child is due for their WCC visit, parents who have not yet scheduled a WCC visit for up to 30 days (for 5-month-olds) or 60 days (for all other ages) after their child is due for a visit will be randomly assigned to two groups with a random number generator. One group will receive an email reminder, while the other group will not receive any reminder.

The randomization of participants to different conditions will be in place until 800 participants have been identified and randomly assigned to one of the arms (estimated sample to detect at least a 10% absolute difference) or 180 days, whichever comes first. To account for delays in updating clinical databases, the final outcome data will be checked 90 days after the last eligible visit (for a maximum study period of 270 days).

#### Methods

#### Sample

The eligible participants will be parents (or the contact of record) of children aged 5, 8, 11, 14, or 17 months at the time of list generation. The child will need to have no WCC visits scheduled 30 days (for 5-month-olds) or 60 days (for all other ages) after their due date for a WCC (i.e., month 6, 9, 12, 15, or 18) and be currently seen at Pediatric clinics within Geisinger's umbrella (i.e., have at least one prior visit). In addition, the parent will need to have an email address and not have opted out of receiving any system emails.

#### Experimental conditions

A list of eligible participants will be generated each day, and a randomizing function in SQL will assign them to the treatment or control condition. Those in the treatment condition will be sent a reminder email, that tells the parent that their child will be due for a WCC in four weeks,

emphasize the importance of these visits, and provide contact information for them to schedule an appointment, as well as a convenient hyperlink for those with online patient portal access. Those in the control condition will not be sent a reminder email.

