#### Outcome measures

The primary outcome measure will be a binary variable indicating whether a WCC visit was scheduled 30–60 days from the email, as determined by billing code; in the absence of a billing code, either a visit type or reason that mentions WCC will be included.

The secondary outcome measures will be a binary variable indicating whether a WCC visit was completed 30–60days from the email (as established by billing codes) and a binary variable indicating whether the child's immunization status is up to date 60 days from the email (as established by the absence of immunization care gaps in the record).

Additional data that will be collected will include email opens, scheduling follow-up WCC visits (i.e., 61–150 days after the email), having any General Pediatrics visit 30–60 days from the email, having any office visit 30–60 days from the email, and immunization status for Measles/Mumps/Rubella vaccine (MMR), Hepatitis A, Hepatitis B, and Varicella.

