#### Primary Research Question: Do reminder emails increase scheduled WCC visits?

H1: Those who received reminder emails will have a higher percentage of WCC visits scheduled compared with those in the control group.

For all analyses, a logistic regression model will analyze the outcomes as a function of condition. The control condition will be the reference group. For all tests, two-tailed p-values < 0.05 will be used to determine statistical significance. Only the first WCC visits of patients within the study period will be analyzed.

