#### **Additional Analyses**

For the primary and secondary analyses, we will conduct separate robustness checks adding immunization status at the day the email was sent as a control variable.

To examine engagement with the email, the percentage of people who opened emails will also be examined.

We will also examine the broader effects of the intervention on engagement with the health system, specifically, General Pediatrics visits and any office visits.

A more distal goal of the project is to get otherwise unengaged parents to continue scheduling WCC visits for their child. Thus, we will also look at the effect of the intervention on WCC visits for the child's next due date.

Finally, immunization for MMR, Hepatitis A, Hepatitis B, and Varicella are of particular interest for the research team, so we will also examine if the intervention individually affected each of those immunization rates.

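### Does the lack of a rule against relisting a child undermine the email versus no-email comparison for the next well-child visit?

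*Combined protocol and SAP*

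**What the plan says.** Assignment is a daily process: "A list of eligible participants will be generated each day, and a randomizing function in SQL will assign them" to one of the two arms (Experimental conditions). The Sample section admits the parents or contacts of "children aged 5, 8, 11, 14, or 17 months at the time of list generation". It adds a scheduling criterion, "The child will need to have no WCC visits scheduled 30 days (for 5-month-olds) or 60 days (for all other ages) after their due date", and requires a prior visit, an email address and no opt-out. None of these refers to earlier assignment.

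The Background places assignment 30 days before the visit is due. Randomisation continues "until 800 participants have been identified and randomly assigned to one of the arms", with a limit of 180 days. The same section says that the comparison group gets no reminder.

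The primary outcome and the completed-visit outcome use days 30–60 after the email; immunisation status is read at day 60. Among the additional data is "scheduling follow-up WCC visits (i.e., 61–150 days after the email" (Outcome measures), which serves to examine the "effect of the intervention on WCC visits for the child's next due date" (Additional Analyses). On repeats, the Statistical Analysis Plan says: "Only the first WCC visits of patients within the study period will be analyzed".

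**The concern.** A query that returns everyone who meets the listed criteria will return the same child again at the next eligible age if that visit is also unbooked. The child would then be randomised afresh. A control could receive an email about the next visit, and a treated child could receive a second one.

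That next visit is the target of the 61–150 day outcome, so the later email falls inside the measurement window. The next-visit comparison might then no longer be a clean test of one email against none. If controls were relisted more often than treated children, the difference between arms would shrink. It could also be asked whether a repeat assignment counts toward the 800.

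**Working it through.** **The plan's own figures.** The maximum study period is 180 + 90 = 270 days, as stated. The target of 800 is consistent with a 10-point difference under assumed inputs, since the plan gives no power, control rate or allocation ratio. With 45% vs 55%, two-sided 0.05, 80% power and 1:1 allocation:

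n per arm = (1.96·√(2·0.5·0.5) + 0.8416·√(0.45·0.55 + 0.55·0.45))² / 0.10² ≈ 392, or 784 in total.

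The relisting question does not depend on this figure.

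**Timing.**
- The gap between eligible ages is 365.25/4 = 91.3 days (89–92 by calendar).
- The next due date is about day 30 + 91 = 121 after first assignment, inside days 61–150. A second email at about day 91 is also inside.
- A third listing, at about 2 × 91 = 182 days, falls after enrolment closes. A child first listed at 17 months has no later eligible age.
- The H1–H3 windows close at day 60, at least 29 days before the earliest second email (89 − 60).

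**When it can arise.** Relisting needs enrolment to run past about day 91. It cannot occur if accrual exceeds 800/91.3 = 8.8 per day. Reaching 800 only on day 180 means 800/180 = 4.4 per day. The plan gives no accrual rate.

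**How many children.** Assume even accrual over T days and five equal age groups, four of which can recur. The share reaching a second list date is s = (T − 91)/T × 4/5. At 1:1, half of those relisted are emailed.

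| T (days) | s | Emailed again if all are still unbooked (s × 0.5) | If half are still unbooked (s × 0.25) |
|---|---|---|---|
| 91 or less | 0 | 0 | 0 |
| 120 | 29/120 × 0.8 = 19% | 10% | 5% |
| 150 | 59/150 × 0.8 = 31% | 16% | 8% |
| 180 | 89/180 × 0.8 = 40% | 20% | 10% |

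These are scenario values, not upper bounds: earlier-weighted accrual or fewer 17-month-olds would raise them. With equal relisting, they apply to each arm.

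**Effect on the contrast.** Let r_T and r_C be the proportions relisted among those reaching a second date, and e the effect of the second email, taken as equal in both arms. Each arm's outcome rises by s × r × 0.5 × e. The treated-minus-control difference moves by s × 0.5 × e × (r_T − r_C), so equal relisting cancels. With controls relisted 10 points more often and e = 10 points:

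- T = 120: 0.193 × 0.10 × 0.5 × 0.10 = 0.10 points
- T = 150: 0.315 × 0.10 × 0.5 × 0.10 = 0.16 points
- T = 180: 0.396 × 0.10 × 0.5 × 0.10 = 0.20 points

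For 400 per arm and rates near 50%, the standard error is √(2 × 0.25/400) = 3.5 points. The largest of the three shifts is 0.20/3.54 = 0.06 standard errors.

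A 10-point relisting gap implies that the first email had already raised next-visit booking by about 10 points in these children. The shrinkage is then about 0.2/10 = 2% of such an effect.

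**Range.** Setting s = 1 removes the accrual and age-mix assumptions: 1 × 0.10 × 0.5 × 0.10 = 0.5 points, or 0.14 standard errors. Doubling both the gap and the email effect at T = 180 gives 4 × 0.198 = 0.8 points, or 0.22 standard errors.

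**The case for a change.** The strongest case for a change is that the text leaves a real gap. The first-visits rule restricts the analysis, not the daily list, so a child's first record can be kept while its day 61–150 outcome is touched by a second email. The statement that controls get no reminder is not carried into any list criterion. There is also a reason to expect unequal relisting: the Background says that standard care offers the next booking at the end of a visit, so if the email raises attendance, treated families get that offer more often. Continued engagement is a stated, more distal goal, and an exclusion clause would cost little.

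The gap in wording and the dates stand. The inference that the comparison is spoiled does not. The second assignment does not depend on the first arm and reaches both arms. If the first email changes nothing, relisting and second emails are balanced by randomisation, so there is neither bias nor inflated type I error. If it does work, a difference in relisting is one of its consequences, and the contrast by first assignment estimates its effect under the daily-list process. The share of controls emailed is therefore not the bias; only the difference between arms matters.

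As to the 800, the plan counts participants, and the Sample section defines these as people. On that plain reading a repeat listing does not use up a place.

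**Conclusion.** No change follows. This is a missing detail that whoever builds the list would normally fill in the obvious way: one arm per participant, as the Background implies, with analysis by first assignment, which fits the first-visits rule.

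If it were not filled in that way, H1–H3 would still be untouched. What remains is one exploratory outcome with no formal hypothesis and no sample-size claim, and only if enrolment passes about day 91. The expected shrinkage is 0.1–0.2 points for enrolment of 120–180 days, at most 0.06 of a standard error, and it is toward no effect. This rests on 1:1 allocation, even accrual, equal age groups, a 10-point relisting gap and a 10-point second-email effect that is the same in both arms. None of these is given in the documents. The less favourable values tried above stay below one quarter of a standard error, so excluding relisted children would not materially alter any conclusion.

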#### Outcome measures

The primary outcome measure will be a binary variable indicating whether a WCC visit was scheduled 30–60 days from the email, as determined by billing code; in the absence of a billing code, either a visit type or reason that mentions WCC will be included.

The secondary outcome measures will be a binary variable indicating whether a WCC visit was completed 30–60days from the email (as established by billing codes) and a binary variable indicating whether the child's immunization status is up to date 60 days from the email (as established by the absence of immunization care gaps in the record).

Additional data that will be collected will include email opens, scheduling follow-up WCC visits (i.e., 61–150 days after the email), having any General Pediatrics visit 30–60 days from the email, having any office visit 30–60 days from the email, and immunization status for Measles/Mumps/Rubella vaccine (MMR), Hepatitis A, Hepatitis B, and Varicella.

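### In four of the five age cohorts the scheduled and completed outcomes close 30 days before the entry rule does, so the day-60 result cannot separate more scheduling from earlier scheduling

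*Combined protocol and SAP*

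**What the plan says.** **Timing.** The Background section generates the list and randomises "30 days before a child is due for their WCC visit". The email itself (Experimental conditions) tells the parent that "their child will be due for a WCC in four weeks".

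**Entry.** A family is eligible only if no WCC is already booked "up to 30 days (for 5-month-olds) or 60 days (for all other ages) after their child is due for a visit" (Background). The Sample section gives the same limits: "30 days (for 5-month-olds) or 60 days (for all other ages) after their due date".

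**Outcomes.** Under Outcome measures, the primary outcome is "a binary variable indicating whether a WCC visit was scheduled 30–60 days from the email" and the first secondary outcome is "a binary variable indicating whether a WCC visit was completed 30–60days from the email". Neither has an age-specific limit. The same section collects follow-up WCC scheduling on days 61–150 after the email, and the SAP's Additional Analyses describe this as the effect on visits for the next due date.

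No section explains why the entry limit varies with age and the outcome limit does not.

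**The concern.** The plan uses two conventions for when a visit still belongs to the current due date. Take an 11-month-old with a WCC on email day 75. If the visit was booked before list generation, the child already has the current visit and is not randomised. If it is booked after randomisation, the child has no event on H1 (appointment-date reading) and none on H2 even if the visit is attended. The same appointment then counts as engagement with the next due date.

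H1 and H2 claim higher percentages scheduled and completed. With the window closed at day 60, two different effects can produce or hide a difference. Extra visits that fall on days 61–90 do not count towards it. Visits that would have taken place on days 61–90 anyway, and are only moved earlier, count as gains. The follow-up outcome is blurred as well, because it mixes late current visits with visits for the next due date.

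**Working it through.** **Inputs from the documents:** email 30 days before the due date (Background); entry limits of due date + 30 or + 60 days (Background, Sample); outcome window of days 30–60 and follow-up window of days 61–150 (Outcome measures). Controls get no email, so I take their day 0 to be the list date.

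**Step 1: put everything on the email clock.** Due date = day 30. Entry limit = 30 + 30 = day 60, or 30 + 60 = day 90.

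| Cohort | Entry rule closes | Outcomes close | Uncovered |
|---|---|---|---|
| 5 months | day 60 | day 60 | none |
| 8, 11, 14, 17 months | day 90 | day 60 | days 61–90 (30 days) |

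With the email's four weeks (28 days) the limits become days 58 and 88, and the uncovered stretch in the older cohorts is days 61–88 (28 days).

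**Step 2: where days 61–90 go.** They lie inside the 61–150 day follow-up window. For the 8-, 11- and 14-month cohorts the next listed due date is three months after the current one, near email day 120 with 30-day months. In the four older cohorts the plan therefore treats days 61–90 as current at entry and as next at outcome.

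**Step 3: the plan's own figure.** The Background gives 800 participants for a 10-point difference, without a control rate or power, so 800 cannot be derived from stated inputs. It is consistent with usual choices: 45% v 55% at 80% power, two-sided 0.05, needs 784. The mismatch does not depend on this figure.

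**Step 4: illustrations.** All of the following are assumptions, not figures from the documents: five equal cohorts, 400 per arm, and day-90 rates as stated. Power is from the normal approximation with pooled variance under the null.

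*Dilution.* True rates over the entry-rule window are 45% v 55%. A share s of visits in the four older cohorts falls on days 61–90, equally in both arms. Each observed rate is the true rate × (1 − 0.8s).

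| s | Observed rates | Difference | Power |
|---|---|---|---|
| 0 | 45.0% v 55.0% | 10.0 points | 80.9% |
| 10% | 41.4% v 50.6% | 9.2 points | 74.3% |
| 20% | 37.8% v 46.2% | 8.4 points | 67.3% |
| 30% | 34.2% v 41.8% | 7.6 points | 60.1% |

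*Acceleration only.* Both arms reach 50%. In the four older cohorts the late share is 30% in controls and 10% with the email.

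- Control by day 60: 50 × (1 − 0.8 × 0.30) = 38%.
- Email by day 60: 50 × (1 − 0.8 × 0.10) = 46%.
- Difference: 8 points at day 60, none over the entry-rule window. The day-60 test would be significant about 63% of the time.

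**The case against.** **Different limits are not in themselves an error.** The entry rule selects whom to contact; the endpoint defines what is measured. A visit within 30 days of the due date is a legitimate estimand, and it applies equally to both arms. This stands. A reader might infer that the mismatch biases the trial; the documents do not support that, since randomisation and the day-60 comparison are intact.

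**Visits on days 61–90 are not lost.** A reader might infer that they drop out of the data. They do not: the follow-up outcome records them and the SAP compares it by arm. What remains is that they are attributed to the next due date and mixed with visits that really belong there.

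***Scheduled* may date the booking act.** The text does not say. On that reading a day-75 appointment booked on day 40 would count for H1, while a booking made in the first 29 days would not. The completed-visit and follow-up windows make the appointment date the more natural reading, but for H1 the point depends on it. H2 is affected on either reading.

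**Moving the primary window has its own costs.** A reader might infer that day 60 must be replaced by day 90. That does not follow. A day-90 primary would overlap the follow-up window, and it would leave the day-60 immunization outcome and the day 30–60 General Pediatrics and office-visit outcomes on a different time frame. Nor would it match the entry rule fully: the Background wording appears also to cover visits booked before the due date, yet days 1–29 produce no outcome event at any age. This objection stands, and it is why the remedy is an added analysis.

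**Conclusion.** The mismatch is real and follows from the plan's own dates: no gap at 5 months and 30 days (28 on the email's wording) in the other four cohorts. It holds for H2 as written, and for H1 if *scheduled* refers to the appointment date. The consequence concerns interpretation. A day-60 difference is a valid randomised result about visits by day 60, but alone it does not show that more children get the visit the entry rule says they lack.

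The size is unknown. The documents give no share of visits on days 61–90, and the two illustrations push in opposite directions, so neither the losses of 0.8 to 2.4 points nor the 8-point apparent gain should be read as an estimate for this trial. They show only that modest shares of late visits would matter in a trial sized for 10 points.

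**What to change.** The SAP states that enrollment has not begun and no data have been examined, so these are wording changes:

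- State that the 30–60 day window refers to the appointment date. Day 30–60 may stay primary.
- Pre-specify a named analysis of H1 and H2 with the window closing at day 60 for 5-month-olds and day 90 for the 8-, 11-, 14- and 17-month cohorts.
- State in advance that a day-60 difference that disappears at day 90 will be reported as earlier scheduling, not additional scheduling.
- Start the follow-up window after day 90 in the four older cohorts, so that no visit counts as both current and next.

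**Cost.** One more analysis from the same records. The final data pull also needs care: a child randomised on study day 180 reaches day 90 on study day 180 + 90 = 270, which is the stated maximum study period and leaves no room for database lag. The follow-up outcome already raises this, since day 150 for the same child is study day 180 + 150 = 330, so later data are needed in any case.

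### The day 61–150 follow-up outcome does not isolate visits for the next due date, and a 270-day study cannot fully observe it if enrolment lasts 180 days

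*Combined protocol and SAP*

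**What the plan says.** Among the additional data, Outcome measures lists "scheduling follow-up WCC visits (i.e., 61–150 days after the email", with one window for every age. The SAP's Additional Analyses section gives the purpose: "we will also look at the effect of the intervention on WCC visits for the child's next due date".

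The timeline comes from Background and Sample. The email is sent 30 days before the current due date. Children are eligible if no current visit is booked "for up to 30 days (for 5-month-olds) or 60 days (for all other ages) after their child is due for a visit"; Sample repeats the rule as "no WCC visits scheduled 30 days (for 5-month-olds) or 60 days (for all other ages) after their due date for a WCC". The due ages are listed as "i.e., month 6, 9, 12, 15, or 18".

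Enrolment stops at 800 participants or at 180 days. On the data check, Background says that "the final outcome data will be checked 90 days after the last eligible visit (for a maximum study period of 270 days", and gives the reason: "To account for delays in updating clinical databases".

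**The concern.** Two things do not line up with the stated purpose.

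First, the window opens on day 61, only 31 days after the current due date. A child who misses the day 30–60 primary window and attends the overdue visit on, say, day 75 is a failure on the primary outcome and a success on the follow-up outcome, although no visit for the next due date has taken place. No section separates the two kinds of visit. The SAP's restriction to first WCC visits does not do so either, because the late current visit may itself be the first.

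Second, the outcome needs 150 days of follow-up per child, and the stated maximum study length does not provide that for children emailed late in a full-length enrolment period.

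At stake is the interpretation of one additional analysis. A difference between arms could be reported as an effect on continued care at the next due date when part of it reflects catching up on the current visit, and some children would not have been followed long enough to contribute fully.

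**Working it through.** **Inputs.** Email = day 0; current due date = day 30; due ages 3 months apart; screen for a booked current visit to 30 days (5-month-olds) or 60 days (other ages) after the due date; follow-up window = days 61–150; enrolment at most 180 days; maximum study period 270 days. A month is taken as 30.44 days.

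**1. The plan's own figure.** 180 + 90 = 270, exactly. This works only if the 90 days run from the last email. If the last eligible visit is a visit on day 60 after the last email, the sum is 180 + 60 + 90 = 330, which does not match 270.

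**2. Where the window sits.**
- Next due date (5-, 8-, 11- and 14-month cohorts): 30 + 3 × 30.44 = day 121.3 (day 120 with 30-day months).
- Window opens: 61 − 121.3 = about 60 days before it. Window closes: 150 − 121.3 = about 29 days after it.
- End of the current-visit screen: 30 + 30 = day 60 for 5-month-olds; 30 + 60 = day 90 for all other ages.
- Overlap of screen and window for the older four cohorts: days 61–90, which is 30 of 90 days (33%).
- Midpoint of the two due dates: (30 + 121.3)/2 = day 75.7. Days 61–75 (15 of 90) are therefore nearer to the current due date than to the next one.
- For 5-month-olds the screen does not overlap the window, but a late 6-month visit on days 61–90 is still counted, at least 30 days before the 9-month due date.

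**3. Whether day 150 is reached.**
- Under the 270-day maximum, the last email day with day 150 observed is 270 − 150 = study day 120.
- With 180 days of enrolment, emails on days 121–180 fall short: 60/180 = 33% if enrolment is even (assumption), or about 267 if all 800 are enrolled.
- The last child is seen to 270 − 180 = day 90, so only the overlapping days 61–90 of the window have elapsed.
- Full observation needs study day 180 + 150 = 330, which is 60 days past the maximum.

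**4. If enrolment stops earlier, on day E.** The answer depends on how the timing of the check is read (even enrolment assumed):

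| E | Check at E + 90: share short of day 150, min(1, 60/E) | Check at E + 60 + 90, capped at 270: share short, max(0, E − 120)/E |
|---|---|---|
| 180 | 33% | 33% |
| 120 | 50% | 0% |
| 90 | 67% | 0% |
| 60 | 100% | 0% |

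In the second column of shares, the check falls on day 150 of the last child's follow-up (day 120 + 150 = 270 at E = 120). Day 150 is reached, but with no days left for the database delay that the 90 days are meant to cover.

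**The case against.** **The window contains the next due date.** This stands. A reader might infer that the outcome fails to measure next-due-date visits at all. That is too strong: for four cohorts the window includes the date and 29 days beyond it. The randomised comparison is valid for any WCC on days 61–150, and that partly serves the aim of keeping parents engaged. What is missing is separation from late current visits.

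**The screen is an eligibility rule, not an outcome definition.** Also fair. By the outcome windows alone, the current visit is days 30–60 and follow-up adjoins it without a gap. The calendar is unchanged, however: days 61–90 are 31 to 60 days after one due date and at least 30 days before the next.

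**The shortfall depends on a reading.** Partly right. A reader might take the 50%, 67% and 100% figures as general; they hold only if the check is 90 days after the last email. The 33% at 180 days holds on both readings once the 270-day maximum is applied.

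**Already booked appointments might be captured at the check.** Possibly, since the outcome is worded as scheduling. Bookings made after the check would still be lost.

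**Other inferences to avoid.** Because "Standard care involves scheduling a follow-up WCC visit at the end of the current visit", a reader might take the window as booking dates and conclude that next visits booked on time are missed. Outcome measures identifies scheduled visits by billing code, or else by visit type or reason, so this reading is implausible. Nor do the documents show that the 17-month cohort has no next visit: the due ages are an eligibility list, and they are simply silent on what follows month 18.

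**Conclusion.** The point holds as a minor one. The day 61–150 outcome does not isolate visits for the next due date: one third of its days lie at least 30 days before that date in the 5- to 14-month cohorts, and the same days lie inside the plan's current-visit screen for every age except 5 months. If enrolment lasts 180 days, the 270-day maximum leaves children emailed after study day 120 incompletely observed.

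The overlap rests only on the plan's calendar. The 33% adds two assumptions: even enrolment and the full 180 days. For shorter enrolment, the shortfall ranges from none to all children, depending on how the last eligible visit is read.

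A reader might infer a bias of known size or direction. The documents do not support that: they give no rate of late or next visits in either arm, and the truncation applies to both arms. H1, H2 and H3 use other windows and are unaffected.

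**What to change.** For this additional outcome only:

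1. Extract its data at least 150 days after the last email, plus an allowance for database delay, and reconcile the wording on the last eligible visit with the 270-day maximum.
2. Label days 61–150 as *any later WCC*.
3. Beside it, report WCC visits on days 91–150, by visit date, in the 5-, 8-, 11- and 14-month cohorts as the next-due-date measure. Show the 17-month cohort separately unless a next due date is stated for it.

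Leave the primary and secondary windows as they are.

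**Cost.** Changes to wording and queries, and a later extraction: at study day 330 or after if enrolment runs 180 days, which is 60 days or more past day 270. The plan's own figures suggest an allowance between 30 days (270 − 240, what the maximum leaves after the last child's day 60) and 90 days (the stated interval), which gives study day 360 to 420. The day 91–150 measure has limits of its own: it misses early next visits on days 61–90 and still counts current visits made after day 90. This is why it should stand beside the wider window and not replace it.

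### The follow-up scheduling outcome (days 61–150) runs past the entry check for booked visits, so appointments made before assignment can count as follow-up scheduling and dilute the effect

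*Combined protocol and SAP*

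**What the plan says.** All passages are in the combined protocol and SAP.

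- **Timing (Background).** The list is drawn and the email sent "30 days before a child is due for their WCC visit", so the due date is email day 30.
- **Entry check (Background; Sample).** Parents enter if no WCC visit is booked "for up to 30 days (for 5-month-olds) or 60 days (for all other ages) after their child is due for a visit". Sample states the same horizon without the words for an upper limit: "no WCC visits scheduled 30 days (for 5-month-olds) or 60 days (for all other ages) after their due date for a WCC".
- **Follow-up outcome (Outcome measures).** The additional data include "scheduling follow-up WCC visits (i.e., 61–150 days after the email"), with one window for all ages and no condition on when the booking was made.
- **Its purpose (Additional Analyses).** The distal goal is to "get otherwise unengaged parents to continue scheduling WCC visits for their child", and for that reason "we will also look at the effect of the intervention on WCC visits for the child's next due date".
- **Primary outcome, for comparison (Outcome measures).** It is "whether a WCC visit was scheduled 30–60 days from the email, as determined by billing code", with visit type or reason as the fallback. No booking date is mentioned.

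**The concern.** The primary outcome has a safeguard that the follow-up outcome lacks. The primary window, days 30–60, lies inside the period that must be free of bookings at entry, so a visit found there was booked after assignment. Most or all of the follow-up window lies beyond that period. A child can therefore enter the trial already holding an appointment inside the follow-up window, and nothing in the plan removes it. The rule that only first WCC visits are analysed says nothing about booking dates.

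The interpretation of the distal-goal analysis is at stake. That analysis asks whether the email leads otherwise unengaged parents to keep scheduling. A parent who already holds a booking for the window fits that description poorly, and the booking cannot be a result of the email. Mixing such children in blurs what the outcome measures and pulls the difference towards zero.

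**Working it through.** **1. Windows, in email days**

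- Due date: day 30 (Background).
- Entry check ends, 5-month-olds: 30 + 30 = day 60.
- Entry check ends, other ages: 30 + 60 = day 90.
- Follow-up window: days 61–150, which is 150 − 61 + 1 = 90 days.
- Unscreened, 5-month-olds: days 61–150, 90 of 90 days.
- Unscreened, other ages: days 91–150, 60 of 90 days. Days 61–90 are covered by the entry check.
- Next due date: the due months in Sample are three months apart, so about 30 + 3 × 30.4 = day 121. For every age with a next visit on that spacing, this falls in the unscreened part.

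**2. The plan's own sample size (context only)**

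The plan gives 800 participants for a 10-point absolute difference, without a control rate or power. With two-sided 0.05, 1:1 allocation and an assumed 80% power, 40% vs 50% needs 776 in total (816 with continuity correction) and 45% vs 55% needs 784 (824). The figure of 800 is therefore consistent with a control rate near 50%. That supports 400 per arm and 40% vs 50% as an illustration. The plan claims no power for the follow-up outcome.

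**3. Dilution**

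Let q be the share of children with a WCC visit already booked for the window on list day, equal in expectation in both arms because it is fixed before randomisation. Assume that every such booking scores 1. With p the rate among the remaining children:

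- observed rate in an arm = q + (1 − q)p
- observed difference = (1 − q) × (p₁ − p₀)

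Power is the two-proportion normal approximation, Φ[(d − 1.96·SE₀)/SE₁], with pooled SE₀ and unpooled SE₁. There are 400 per arm as written and 400(1 − q) per arm when children with a prior booking are left out.

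Example, q = 5%:

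- Rates: 0.05 + 0.95 × 0.40 = 0.430 and 0.05 + 0.95 × 0.50 = 0.525, so d = 0.095.
- SE₀ = 0.0353 and SE₁ = 0.0352, giving Φ(0.733) = 0.768.
- Restricted: 380 per arm, 0.40 vs 0.50, giving Φ(0.815) = 0.792.

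| q (assumed) | Observed rates | Difference (points) | Power as written | n per arm, restricted | Power restricted |
|---|---|---|---|---|---|
| 0 | 40.0% vs 50.0% | 10.0 | 81.3% | 400 | 81.3% |
| 1% | 40.6% vs 50.5% | 9.9 | 80.4% | 396 | 80.9% |
| 2% | 41.2% vs 51.0% | 9.8 | 79.5% | 392 | 80.5% |
| 5% | 43.0% vs 52.5% | 9.5 | 76.8% | 380 | 79.2% |
| 10% | 46.0% vs 55.0% | 9.0 | 72.2% | 360 | 77.1% |

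The documents give no value of q, so the table shows a range and not an estimate.

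**The case against.** **The window may refer to the act of booking.** The phrase could mean that the booking is made on days 61–150, and earlier bookings would then never count. The wording allows this, and the plan should settle it. The appointment-date reading is much the better one, for three reasons. The primary outcome is determined from billing codes. Additional Analyses speaks of visits for the next due date. Background says that "Standard care involves scheduling a follow-up WCC visit at the end of the current visit", so a parent who attends around days 30–60 would book the next visit then, and a booking-date window would miss most follow-up bookings.

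**A prior booking is not a settled outcome.** A reader might infer that these children have their result fixed at 1 on the day of assignment. The documents do not support that. The follow-up outcome has no ascertainment rule of its own. If the primary outcome's rule applies, the score depends on what the record later shows, and a booked visit can be cancelled, missed or moved. Scoring every prior booking as 1 is a simplifying assumption of the table.

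**The group is probably small.** Standard care books one visit ahead, and the trial enrols parents with nothing booked through day 60 or 90. For four of the five age groups, a child must have nothing booked through day 90 and still hold a visit on days 91–150. This stands, and it is why the low values of q belong in the table. Some of these bookings may also be the current visit arranged late, which raises the separate question of which due date a visit in the window serves.

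**The all-randomised comparison is valid.** A reader might infer bias or an inflated false-positive rate. Neither follows, because prior bookings are fixed before randomisation and fall on both arms alike. Comparing all randomised children on visits for the next due date is a legitimate question. The restricted analysis answers a narrower one, closer to the stated interest in unengaged parents, so both results are worth reporting.

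**Conclusion.** The point holds as a minor one. Under the appointment-date reading, the entry check leaves the whole follow-up window open for 5-month-olds and two thirds of it (60 of 90 days) for the other ages, and no passage removes visits booked before assignment. The consequence is dilution that affects both arms alike: the difference shrinks by about the fraction q. Restriction gains about 0.5 to 1 point of power at q = 1–2%, about 2.4 points at q = 5% and about 5 points at q = 10%. These figures assume 400 per arm, 40% vs 50% among children without a prior booking, and prior bookings that all score 1 in both arms. The true q is unknown and may be near the low end. The gain from a change is therefore small and uncertain. Only one additional outcome is involved; the primary and secondary hypotheses are untouched.

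**What to change.** For the follow-up scheduling outcome only:

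1. State in Outcome measures that days 61–150 refer to the appointment date.
2. On list-generation day, record whether a WCC visit is already booked for days 61–150 after the email.
3. In Additional Analyses, compare the arms among children without such a booking. The flag is fixed before assignment, so the restriction preserves randomisation.
4. Report the number excluded in each arm, and give the all-randomised result alongside.

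The cost is one extra field in the record pull, a sentence or two in the plan and a slightly smaller denominator for one additional analysis. The SAP states that enrolment has not begun and no data have been examined, so under the plan as written the change can be made before any result is seen. The primary and secondary analyses stay as they are.
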